## **4.2 Randomization and blinding**

### **4.2.1 randomize**

In this study, patients meeting the inclusion criteria will be randomized into the trial group and the control group in a 1:1 ratio.

Random numbers generated by SPSS software were used to include eligible subjects.

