1.1.3.2 Neuroelectrophysiological assessment: The most commonly used neuroelectrophysiological evaluation methods are: Electroencephalo Graphic (EEG), Evoked Potential (EP) and transcranial magnetic stimulation combined with electroencephalographic (TMS-EEG). Conventional EEG is widely used to evaluate the prognosis of coma patients by analyzing the frequency, amplitude and waveform of brain waves [9] to evaluate brain function. When the brain tissue is damaged, the rhythm of the brain will change correspondingly, the brain activity slows down, and is proportional to the severity of the injury, mostly from the normal rhythm of  $\alpha$  waves into the slower frequency of  $\delta$  waves and  $\theta$  waves. EP

has strong objectivity and can avoid the disturbance caused by sleep. Clinically, Brainstem Auditory Evoked Potentials (BAEP) and Somatosensory Evoked Potentials, SEP) and Event Related Potential (ERP) are the most commonly used evoked potentials and can be used to evaluate the prognosis of patients with DOC.BAEP stimulates the ear through sound and induces electrical activity of nerve cells through electrode conduction, which is not affected by physiological changes or drug factors of patients, and can directly reflect the function of the brain stem, but cannot show the function of the cerebral cortex. However, a few coma patients have no brain stem damage and their auditory function can still work normally, and BEAP may be normal at this time. However, in patients with prolonged latency and reduced wave amplitude, or disappearance of wave V, about 90% of these patients will have a severe poor prognosis or death, or a long-term VS state.

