### **5.2 inclusion criteria:**

(1) sign the informed consent voluntarily;

(2) met the above diagnostic criteria, and the GCS score was between 3 and 9 (the score was scored by a rehabilitation physician, and the patient had not used sedatives or anesthetics on the day of the score);

- (3) The patient's condition is stable, vital signs are stable, and the onset time of consciousness disturbance caused by stroke is confirmed to be less than 6 months;
- (4) Cerebral infarction or cerebral hemorrhage confirmed by clinical and auxiliary examination is the only factor causing consciousness disorder, excluding other diseases caused consciousness disorder patients;
- (5) those aged between 18 and 85;
- (6) Family members or authorized principals know and sign informed consent;
- (7) did not enter other clinical studies at the same time.

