### **13.3 Statistical method**

The analysis included case distribution, demographic data, baseline analysis and therapeutic effect analysis. Baseline data included sex, age, stroke type, stroke duration, underlying medical history (diabetes, hypertension, heart disease, chronic obstructive pulmonary disease), and history of smoking and alcohol use. Baseline data were tested by chi-square test. The end point data was the score of the State of Consciousness scale, and the measurement data was expressed as mean SD. Univariate analysis of variance was used to compare the difference between groups at the same time point, the difference at different time points in the group, and the difference before and after between the two groups.  $P < 0.05$  was considered statistically significant, and multiple comparisons were performed by Dunnett-t test.

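### Baseline BAEP, which the protocol itself treats as strongly prognostic, is measured before treatment but left out of the between-arm comparison, so available precision is given up

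*Combined protocol and SAP*

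**What the plan says.** **Allocation.** Section 4.2.1 states that "patients meeting the inclusion criteria will be randomized into the trial group and the control group in a 1:1 ratio", and adds only: "Random numbers generated by SPSS software were used to include eligible subjects". No block, stratum or minimisation factor is described there or elsewhere.

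**Who enters.** Section 5.2 requires that "the onset time of consciousness disturbance caused by stroke is confirmed to be less than 6 months", with no lower limit, and admits both infarction and haemorrhage: "Cerebral infarction or cerebral hemorrhage confirmed by clinical and auxiliary examination is the only factor causing consciousness disorder".

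**What is known at baseline.** The background, section 1.1.3.2, singles out two BAEP patterns: prolonged latency with reduced amplitude, or loss of wave V. Of patients with these it says "about 90% of these patients will have a severe poor prognosis or death, or a long-term VS state". Both the flow chart and section 7.2(2) place a BAEP examination before the intervention. They differ on when the second one is done, but that does not affect the baseline reading. Section 13.3 lists stroke type and stroke duration among the baseline data. BAEP is not on that list.

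**How the arms are compared.** Section 13.3 states: "Univariate analysis of variance was used to compare the difference between groups at the same time point". The same method covers within-group changes and before-after differences. The summary and section 13.4 repeat it. None of the three places names a covariate. Baseline variables are tested by chi-square.

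**The concern.** The protocol names a baseline finding that, on its own account, separates patients with a very poor outlook from the rest. It pays to measure that finding in everyone, and then uses it in neither allocation nor analysis. Two patients with the same starting GCS may differ in BAEP status, so a before-after comparison, which brings in baseline GCS, does not stand in for it.

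Two things are at stake. A strong predictor left out of the model stays in the residual variance, so the trial is less precise than its data allow. And if the arms happen to differ in the share of patients with the poor sign, the planned comparison cannot correct for it. A chi-square test can flag such a difference but does not adjust for it, and here BAEP would not even be tested.

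**Working it through.** **1. The plan's own figure.** Section 13.1 gives P1 = 0.794, P2 = 0.548, U values of 1.96 and 1.28, and hence P = 0.671.

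n = 2 × (1.96 + 1.28)² × 0.671 × 0.329 / 0.246² = 76.6 per arm (stated: about 76).

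76 × 1.15 = 87.4, which gives the stated 87 per arm and 174 in total. With 15% dropout, 87 × 0.85 ≈ 74 evaluable per arm. Power on the stated rates is 94% at 87 per arm and 90% at 74.

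**2. Is the unadjusted comparison valid?** The documents give no usable outcome gap by BAEP status, so gaps were assumed. The setting was a binary predictor with 50% prevalence, an overall control rate of 54.8%, and responder rates differing by 20, 40 or 60 points between good- and poor-prognosis patients. Each setting had 40,000 simulated trials with equal arms. With no true effect, the unadjusted two-proportion test at 87 per arm rejected in 5.6–5.7% of trials, and a stratified (CMH) test in 4.9–5.0%. At 36 per arm the unadjusted figure was 4.3–4.6%. Overall error is therefore close to nominal.

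**3. What happens in a trial that is out of balance?** By exact binomial calculation at 87 per arm, with prevalence of 30–50%, the arms differ by at least 10 points on such a predictor in 16–20% of trials, and by at least 15 points in 2.5–4%. Given a difference of at least 15 points and no true effect:

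| Assumed gap | Unadjusted rejects | Stratified rejects |
|---|---|---|
| 20 points | 8% | 5% |
| 40 points | 16% | 6% |
| 60 points | 28% | 5% |

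Such trials are uncommon at the planned size, but adjustment protects against them.

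**4. Precision gained.** With the planned effect of 24.6 points:

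| Evaluable per arm | Assumed gap | Power, unadjusted | Power, stratified |
|---|---|---|---|
| 74 | 20 points | 90% | 91% |
| 74 | 40 points | 90% | 95% |
| 36 | 20 points | 63% | 63% |
| 36 | 40 points | 63% | 71% |

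The 36-per-arm rows are shown because section 4 gives a total of 72 patients, against 174 in the summary and section 13.1. At that size a difference of at least 10 points on one predictor occurs in 37–41% of trials.

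**5. Limit of this check.** Steps 2 to 4 use responder rates, because those are the only outcome figures in the plan. The planned comparison is of GCS scores. There, the variance of the arm difference falls by a factor of about 1 − R², where R² is the share of within-arm variance in week-4 GCS that the added covariates explain. The documents do not give R².

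**The case against.** The strongest reply is that randomisation error is already in the standard error. At 87 per arm the unadjusted difference has SE √(2 × 0.548 × 0.452 / 87) = 7.5 points, so 95% limits of about ±14.8 points. Any shift from a chance BAEP imbalance is part of that 14.8, not a bias on top of it. This stands. A reader might infer from the missing strata and covariates that the trial is biased or its type I error inflated; step 2 shows it is not.

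Four further objections also stand:

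- **The 90% figure is not a responder rate.** A reader might turn it into a 10% effective rate. Section 8.1.1 counts an improvement of 15% or more as effective. One point is enough from GCS 3 to 6 (1/6 = 16.7%), and two points from 7 to 9 (2/9 = 22.2%; 1/7 = 14.3% falls short). Section 1.1.1 notes that vegetative patients may open their eyes, so a patient who stays in that state could still count as effective.
- **Only BAEP has a documented prognostic figure.** That recovery differs by time since onset, or between infarct and haemorrhage, is plausible but nowhere stated. Section 5.2 also requires a stable condition, which limits very early entry.
- **Unrestricted allocation is an inference from silence.** Section 13.1 speaks of 87 cases assigned to each group, which fits a fixed list. The text does not support calculations of unequal arm sizes.
- **Stratified allocation is a trade-off.** No cut-point for time since onset can be drawn from the documents.

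None of this answers the core point: the protocol calls BAEP strongly prognostic, measures it before treatment and then ignores it in the comparison.

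**Conclusion.** The point holds as one of efficiency and robustness, not validity. The between-arm analysis omits a baseline predictor that the protocol itself presents as strong. On assumed gaps of 20 to 40 points at 50% prevalence, using it would raise power at 74 evaluable per arm from about 90% to between 91% and 95%. It would also hold the error rate near 5% in the small fraction of trials that come out clearly unbalanced. With a smaller gap or a rarer sign the gain would be less, and its size for GCS scores cannot be computed from the documents.

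The text does not establish that the design is defective for want of stratification, or that time since onset and stroke type drive recovery here. Those two variables belong in the model because they are already recorded and cost almost nothing. The case itself rests on BAEP.

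**What to change.** In section 13.3, and in the matching text of the summary and section 13.4, replace the between-arm analysis of variance for week-4 GCS with a prespecified ANCOVA that contains treatment arm and:

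- baseline BAEP status, defined as in section 1.1.3.2 (prolonged latency with reduced amplitude, or wave V absent, versus neither), from the pre-treatment reading only;
- stroke type (infarction or haemorrhage);
- stroke duration, as a continuous variable.

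Fix the model before any unblinded analysis, and state how a missing or unreadable baseline BAEP is handled. This can still be done for patients already randomised. Whether baseline GCS also enters is a separate question and does not alter this change.

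Section 4.2.1 should also say whether the random list is blocked or stratified. Stratified blocks are an option, not a requirement of this point.

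The cost is small: no new visits, tests or patients, one missing-data rule, and three degrees of freedom (with 2 × 74 = 148 evaluable patients, residual degrees of freedom go from 146 to 143).

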### **4.2.2 Blind state/broken blind**

Because of the particularity of acupuncture treatment, it is impossible to implement double blindness, so this study implemented single blindness. The realization of single blind conditions: false acupoint method, and Tongyuan acupuncture method are adopted acupuncture methods so that patients and family members do not know the grouping. Moreover, trial designers, scale evaluators, acupuncture operators, and data statisticians do not know the status of treatment groups of individual subjects.

Blindness is crucial to the integrity of this clinical study. However, in the event

of a medical emergency or pregnancy event in an individual subject, the information about the study treatment received by the subject is so important to the subject's management that the treating physician will need to de-blind the subject.

Before blinding a subject's treatment, the investigator should determine that this information is necessary, that it will change the subject's immediate treatment. In many cases, especially when the subject's emergency condition is clearly unrelated to the study protocol, it can be assumed that the subject is being treated with the active drug without the need for blind treatment.

The need for blindness should first be discussed with the responsible medical monitor before determining the best response.

After unblinding, the subjects will withdraw from the study and terminate treatment. Safety follow-up and survival follow-up are still required.

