### **6.3 Treatment methods:**

experimental group selected points: Baihui, Zhongwan, Guanyuan, Qihai, Tianshu (double); Point selection criteria: the national standard "Name and Location of points" (GB/T12346-2006). Intervention time: once a day, 5 days a week for 4 consecutive weeks. Twenty days in total;

Point selection of the control group: acupuncture treatment was performed 1cm beside the point selection of the experimental group.

**6.4 Intervention discontinuation Indicators:** Subjects will withdraw from the study if they have the following indications during treatment:

- (1) If the patient's condition deteriorates during treatment and there is a possibility

of dangerous events, the clinical observation of the case should be terminated according to the doctor's judgment;

(2) In the course of treatment, the patient's family members give up the clinical treatment halfway, request the doctor in charge to terminate the treatment, and terminate the clinical observation of the case;

(3) The treatment is effective, but the patient's family uses other treatment methods in order to speed up the therapeutic effect, and cannot determine the efficacy of the clinical study, and the clinical observation of the case is terminated.

**6.5 drug combination:** Information on all drug combinations during the study period (generic name, purpose of administration, dose, time of administration, etc.) must be recorded in detail in the case report form. Treatment with other investigational drugs is prohibited during the study period.

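### Section 4.2.2 claims blinded acupuncture operators, which the design cannot deliver, and no rule keeps the operator's knowledge of the group from the scale evaluators

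*Combined protocol and SAP*

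**What the plan says.** Section 4.2.2 gives the blinding position in one paragraph. It first concedes that "it is impossible to implement double blindness, so this study implemented single blindness", and explains that patients and families are kept unaware because both arms receive needling. It then extends blinding to four further roles: "trial designers, scale evaluators, acupuncture operators, and data statisticians do not know the status of treatment groups of individual subjects".

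Section 6.3 defines the arms. The experimental arm is needled at listed standard points (Baihui, Zhongwan, Guanyuan, Qihai and both Tianshu). In the control arm, "acupuncture treatment was performed 1cm beside the point selection of the experimental group". Section 7.2 repeats this, with the same background care and the same schedule in both arms. Section 1.4 adds that the control needles go to the same depth.

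On allocation, Section 4.2.1 says only that the ratio is 1:1 and that "Random numbers generated by SPSS software were used to include eligible subjects". It does not say who holds the list or how the operator learns which sites to use.

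On scoring, Section 5.2 says of the entry GCS that "the score was scored by a rehabilitation physician". The people who score the weekly and follow-up scales are not identified beyond the term scale evaluators in Section 4.2.2.

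**The concern.** An operator who must needle either the listed points or sites 1 cm away has to act on the allocation at every session. The plan therefore states a level of blinding that its own procedure rules out, and a report that repeated the statement would be wrong.

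The practical consequence concerns what the plan leaves unsaid. Staff who know the group need a stated barrier between them and the people who score. The plan treats operators as blind and describes no such barrier. Section 1.1.3.1 classes GCS and CRS-R as behavioural scales, scored by an observer at the bedside. GCS is the primary endpoint and CRS-R a secondary one. The test flow chart schedules both in each of the four treatment weeks, alongside the needling, in a single rehabilitation department. If group knowledge reached a scorer, the between-group comparison would be open to assessment bias. If it reached those who decide on withdrawal, the set of patients analysed could also be affected.

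**Working it through.** The blinding claim rests on no figure in the plan, so there is none to reproduce. The check sets the sections side by side and then looks at how sensitive the endpoint definition is.

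**Step 1: can the operator be blind?**
- Dose frequency is the same in both arms: 5 days a week for 4 weeks, so 5 × 4 = 20 sessions (Sections 6.3 and 7.2).
- Needling depth is the same (Section 1.4 and the summary of the research scheme).
- Background rehabilitation and drug treatment are the same (Section 7.2).
- Needle site differs: listed points or 1 cm beside them (Section 6.3).

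The only feature that separates the arms is the one the operator carries out. The operator could be unaware of the group only if the site were disguised from the person placing the needle. No section describes such a device.

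**Step 2: is the statement consistent with its own section?** Section 4.2.2 says that "it is impossible to implement double blindness" because of the nature of acupuncture, and then lists patients, families, evaluators, operators and statisticians all as unaware of the group. If that list were accurate, the trial would be more than single-blind, and the concession would have no content.

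**Step 3: what stands between operator and evaluator?** Section 4.2.2 names evaluators and operators as two roles and says that evaluators are blind. No section says that the two roles must be filled by different people, that operators may not score, or that operators may not tell evaluators the group.

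**Step 4: how much would one point matter?** Section 8.1.1 defines the improvement rate as (score after − score before) / score before × 100%, with less than 15% counted as ineffective. Section 5.2 admits baseline GCS 3 to 9. For a one-point gain:

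| Baseline GCS | 1 / baseline × 100% | Reaches 15%? |
|---|---|---|
| 3 | 33.3% | yes |
| 4 | 25.0% | yes |
| 5 | 20.0% | yes |
| 6 | 16.7% | yes |
| 7 | 14.3% | no |
| 8 | 12.5% | no |
| 9 | 11.1% | no |

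At baseline 7 to 9 two points are needed (2/7 = 28.6%, 2/8 = 25.0%, 2/9 = 22.2%). One point can therefore decide the category at four of the seven eligible baseline scores. This shows how sensitive the category is. It does not estimate bias, because the documents give no information on how often scoring might lean or by how much.

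**The case against.** The strongest reply is that the plan already separates the roles. The sentence that overclaims for operators also names scale evaluators as distinct and blind, and an informed operator does not by itself unblind a separate evaluator. That stands. A reader might infer that nothing separates informed staff from scoring, or that operators score patients; the documents do not support either. What is missing is a procedure that secures the stated separation.

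A reader might also infer that informed staff decide withdrawals. The documents do not say so. The emergency rule in Section 4.2.2 has the treating physician break the blind when needed, which implies that this physician is blind by default. In Section 6.4 a deteriorating patient is withdrawn when "the clinical observation of the case should be terminated according to the doctor's judgment", with no mention of the operator. Events under Section 8.2 go to the trial designer, who is also listed as blind. The members of the group discussion in Section 8.2 are not named, but that gap is not evidence that operators sit in it.

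Third, a reader might take the one-point result to mean that a small scoring lean flips the trial outcome. It does not. It applies only at baseline 3 to 6, and only to a patient whose unbiased change falls just short of the cut-off. Sections 13.3 and 13.4 plan an analysis of variance on scale scores and specify no test of the Section 8.1.1 category. In that analysis a one-point lean shifts a score and reclassifies nobody.

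None of this rescues the operator claim. If a masking device does exist, the plan would have to describe it.

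**Conclusion.** The point holds as follows. Section 4.2.2 claims operator blinding that the described procedure cannot deliver and that conflicts with the concession in the same paragraph. The plan also gives no rule that keeps the operator's knowledge of the group from evaluators who score observer-rated endpoints.

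The first part follows from the text of Sections 4.2.2, 6.3 and 7.2, on the one assumption that no undescribed masking of needle sites is in use. The second part is a missing safeguard; the documents contain no evidence that evaluators were or will be unblinded. The size of any resulting bias cannot be estimated. The only numerical guide is that one GCS point crosses the 15% line at baseline 3 to 6 and not at 7 to 9, on a category that the planned analysis of variance does not test.

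**What to change.** In Section 4.2.2:

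- Delete acupuncture operators from the list of blinded roles, and state that operators are not blinded, while patients and families, scale evaluators and the statistician are.
- State that scale evaluators are different people from the operators.
- State that operators do not score any scale and do not disclose allocation to evaluators or to those who decide on withdrawal.

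Leave the clinical withdrawal rules in Sections 6.4 and 8.2 unchanged, along with the operators' reporting of needling events such as hematoma or needle dizziness. Such events can be reported without naming the group. Barring operators from those discussions would touch clinical management and is not needed to correct the blinding statement.

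The cost is protocol wording, with the ethics committee approval that Sections 14.3 and 15.1 require for any revision. Evaluators are already a separate listed role, so no extra staff should be needed, provided the two roles are in fact filled by different people. The downside is that the stated level of blinding becomes less favourable.
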